Bioactive Compounds in Watermelon Modulating Oxidative Stress and Inflammation in Elders

NCT03626168

Study Protocol and Statistical Analysis Plan

February 16, 2016

Protocol

Study participants will be randomized to supplement their diets twice daily with either 100% watermelon juice or an isocaloric placebo for four weeks in a double-blind crossover design. Juice and placebo will be provided in two 12-ounce servings, and participants will be asked to consume one dose in the morning and another in the evening with a meal containing dietary lipid. Based on previous studies^{62,87}, two 12-ounce servings of 100% watermelon juice will provide approximately 1g of L-citrulline and 32 mg of lycopene. Pasteurized watermelon juice for this study will be supplied by Frey Farms (Keenes, IL) from Estrella variety melons. To ensure that all juice contains similar concentrations of the bioactive food compounds of interest, each batch will be tested in the Food and Nutrition Research Laboratory at the University of Alabama for lycopene, citrulline, and arginine content.

Two weeks prior to the intervention, during each intervention arm, and during the washout period, subjects will be asked to consume their typical diet of choice with the exception of foods high in lycopene. A list of lycopene-rich foods such as watermelon and tomato products will be provided, and participants will be asked to limit these foods to two servings per day for the duration of the study. Dietary intake will be closely monitored by 4-day food diaries (three weekdays, one weekend day) submitted during the 2-week run-in period and the 2-week washout period as well as by weekly unannounced 24-hour diet recalls during the treatment period.

Subjects will report to the University of Alabama campus for testing as follows:

Run-In	4-Week Regimen of Juice or Placebo		2-Week Washout	4-Week Regimen of Juice or Placebo	
Days 0-14	Beginning of Week 1	End of Week 4	Weeks 5 & 6	Beginning of Week 7	End of Week 10
4-day food diary	Fasting blood sample	Fasting blood sample	4-day food diary	Fasting blood sample	Fasting blood sample
	Anthropometrics	Anthropometrics		Anthropometrics	Anthropometrics
	FMD	FMD		FMD	FMD
	PWV	PWV		PWV	PWV

Weekly: Weight, Blood Pressure, Adherence

During weekly visits and phone calls with study personnel, subjects will be queried about adherence to the protocol and acceptability of the beverages. Adherence will be assessed by log forms with check-off boxes for each dose, return of all juice bottles at weekly visits, and random 24-hour diet recalls. Minimal adherence will be defined as 70% of recommended supplementation of two doses per day for four weeks.

Statistical Analysis

A biostatistician from the University of Alabama will be responsible for generating a block randomization with PROC PLAN in SAS (version 9.2). The randomization scheme will balance genotype in Groups 2 and 3 (those who receive genetic information at the beginning of the intervention). Differences between groups will be evaluated by one-way ANOVA with repeated measures with group as the between-subjects factor and time as the within-subjects factor.

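### The diet rule lets participants eat watermelon, the test food, during placebo and before both baselines; one reworded rule would prevent this (minor)

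*Combined protocol and SAP*

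**What the plan says.** The diet instructions are in the second paragraph of the Protocol section. For the two weeks before the intervention, each intervention arm and the washout, "subjects will be asked to consume their typical diet of choice with the exception of foods high in lycopene". The next sentence adds the detail. It names watermelon, along with tomato products, on a list handed to participants, and sets a cap, not a ban: "participants will be asked to limit these foods to two servings per day for the duration of the study".

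The study dose is in the first paragraph: "two 12-ounce servings of 100% watermelon juice will provide approximately 1g of L-citrulline and 32 mg of lycopene".

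The plan does monitor diet. "Dietary intake will be closely monitored by 4-day food diaries" in the run-in and washout, and by "weekly unannounced 24-hour diet recalls during the treatment period". At weekly contacts "subjects will be queried about adherence to the protocol and acceptability of the beverages".

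The documents do not define a serving, exclude non-study watermelon, or bar listed foods before a baseline visit. The only adherence threshold, 70%, concerns doses of the study beverage. The Statistical Analysis section gives no use for the diet data.

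**The concern.** The trial compares watermelon juice with a placebo within the same person. Its placebo period is most informative if it is free of the test food, and so are the baseline samples and vascular measurements at the start of weeks 1 and 7. Under the cap, watermelon is permitted in all of these phases, up to the same number of servings a day as the study dose itself.

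Two things are at stake. First, the comparator and both baselines may contain the compounds under test. Citrulline matters most here, because watermelon juice is the only item for which the documents give a citrulline content. Second, if a participant eats different amounts of watermelon in the two periods, the contrast actually delivered varies from person to person, which adds noise to the within-person comparison. The protocol tests every juice batch so that the delivered dose is uniform; an unquantified allowance of the same food works against that.

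**Working it through.** The plan states no figure on this point, so there is nothing to reproduce. The check has a textual part and an illustrative part.

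**Text.** The first sentence makes foods high in lycopene an exception to the typical diet. The second names watermelon as such a food and limits it for the whole study. Read as general rule followed by detail, the two mean: eat freely, except that these foods are capped. On that reading watermelon is allowed, within the cap, in run-in, juice, washout and placebo alike.

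**Inputs from the documents.** About 1 g citrulline and 32 mg lycopene in two 12-oz servings (24 oz); a cap of two servings a day; four-week periods (28 days); one recall a week on treatment.

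**Assumptions.** A background serving is 4, 8 or 12 oz of juice equivalent at study-juice strength. The documents give neither a serving size nor the content of the fruit. Recall days are independent and random (the adherence paragraph does call the recalls random), and intake is reported accurately.

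**Content per ounce.** 1000 mg / 24 oz = 41.7 mg citrulline.

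| Assumed serving | 4 oz | 8 oz | 12 oz |
|---|---|---|---|
| Full cap, oz on that day | 8 | 16 | 24 |
| Citrulline, mg | 333 | 667 | 1000 |
| Lycopene, mg | 10.7 | 21.3 | 32 |
| Share of study dose if eaten daily | 33% | 67% | 100% |
| Citrulline averaged over the week if eaten 1 day in 7, mg/day | 48 | 95 | 143 |
| Share of study dose if eaten 1 day in 7 | 5% | 10% | 14% |

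**Equal intake b in both periods.** (1000 + b) − b = 1000 mg. The absolute contrast is unchanged, and likewise for lycopene at 32 mg.

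**Unequal intake.** If the one-day-a-week pattern occurs in only one period, the contrast for that participant is 1000 ± 48, 95 or 143 mg/day. If intake differs by one serving every day, it is 1000 ± 167, 333 or 500 mg/day.

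**What the recalls would show.** One recall a week samples 4 of 28 days (14%).
- Watermelon every day: it appears in all four recalls, so the probability of missing it is 0.
- Watermelon one day a week: P(no recall shows it) = (6/7)^4 = 0.540.

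The large shares therefore go with intake that is visible, and the intake likely to be missed goes with the small shares.

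**The case against.** The strongest reply is that this is a choice of cap over ban, and a legitimate one. Participants supplement a typical diet, the same rule applies in every phase of a randomised crossover, and a baseline on a typical diet will naturally contain some of these compounds. Diaries, recalls and weekly questions already record intake. The percentages rest on assumed serving sizes and on a juice figure extended to the fruit, and nothing suggests that anyone eats the equivalent of 24 oz of juice a day.

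Most of that stands as a limit on severity. It does not remove the point: recording watermelon does not prevent it, intake within the cap is not a deviation, and no action is tied to the records.

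A reader might infer several stronger things that the documents do not support:
- That the two diet sentences contradict each other. The second reads naturally as the detail of the exception in the first; the wording is loose, not contradictory.
- That the treatment comparison is biased. The rule is the same in both periods, and equal intake leaves the absolute contrast intact.
- That large contamination would go unseen. Daily intake should appear in every recall; the 54% miss probability belongs to the pattern averaging 5% to 14% of the dose.
- That the measurable effect must shrink. This would need a response that flattens at higher intake, and the documents give no dose-response.

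**Conclusion.** The point holds as a minor one. As written, the plan permits the test food during placebo and before both baselines, which is avoidable contamination. If intake differs between periods, it also adds within-person noise. The documents give no usual watermelon intake, outcome variability or sample size, so the effect on precision cannot be determined.

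The shares of 33% to 100% are ceilings for someone who eats the whole cap as watermelon every day; the 5% to 14% shares are for the same amount on one day a week. Neither is an expected intake, and both depend on the assumed serving size and juice-strength content. A participant who eats no background watermelon has no overlap from this source.

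**What to change.** State one rule for run-in, both treatment periods and washout: typical diet; no watermelon or watermelon juice apart from the study beverage; all other listed foods rich in lycopene, tomato products included, held to at most two servings a day. Change the food list handed to participants to match.

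Optionally, code non-study watermelon separately from the study beverage in the diaries and recalls already planned, keeping the beverage blinded. Then report by phase the mean non-study lycopene intake and the number and percentage of recorded days with any non-study watermelon. Keep this descriptive. Do not adjust the treatment model for it, since it is measured after randomisation and, on treatment, on only about 4 of 28 days per period.

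The cost is one reworded instruction, a revised list and, if wanted, one table. Participants who like watermelon go without it for about 12 weeks (2 weeks of run-in plus the 10 scheduled weeks), and the diet becomes slightly less typical. Lycopene overlap from tomato products remains; the change removes only the watermelon source and the citrulline that comes with it.

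### The randomisation and analysis text does not match the crossover: Groups 2 and 3 are unexplained, and an undefined between-subjects group leaves the juice-placebo test unidentified.

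*Combined protocol and SAP*

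**What the plan says.** The Protocol section randomises participants to supplement their diets "with either 100% watermelon juice or an isocaloric placebo for four weeks in a double-blind crossover design". Its visit table shows two four-week regimens separated by a two-week washout. Blood, anthropometrics, FMD and PWV are taken at the beginning of Week 1, end of Week 4, beginning of Week 7 and end of Week 10. A further line reads "Weekly: Weight, Blood Pressure, Adherence".

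The Statistical Analysis section makes a biostatistician responsible for "generating a block randomization with PROC PLAN in SAS (version 9.2"). The next sentence is "The randomization scheme will balance genotype in Groups 2 and 3 (those who receive genetic information at the beginning of the intervention"). The only analysis statement follows: "Differences between groups will be evaluated by one-way ANOVA with repeated measures with group as the between-subjects factor and time as the within-subjects factor".

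**The concern.** In a two-beverage, two-period crossover there are two orders, and every participant takes both beverages. Beverage is therefore a within-subject factor, and what is randomised is the order. The Statistical Analysis section names neither. It balances genotype across numbered groups that the rest of the document does not contain, and it tests a between-subjects *group* that it does not define.

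The balancing rule therefore cannot be carried out from the documents, and the analysis sentence does not say which term compares juice with placebo. An analyst would have to decide what *group* is, which visits make up *time*, and which term is tested. Power ranges from about 1% to 80% across those choices, and nothing in the plan prevents them from being made after the data are seen.

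**Working it through.** **Text check.** Numbered groups, genotype and genetic information occur only in the one randomisation sentence, and the visit table has no genetic procedure. *Group* has three candidate meanings: the genetic-information groups (the only groups the section mentions), beverage (the Protocol section uses the phrase "during each intervention arm"), or sequence (what the crossover randomises). *Time* has four levels for blood, FMD and PWV but is weekly for weight and blood pressure.

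**Inputs.** The documents give no sample size, effect, SD, correlation or alpha, so there is no planned figure to reproduce. Assumptions: N = 18, 30 or 42 in total; SD 1; equal correlation ρ = 0.3, 0.5 or 0.7 between all visits; no carryover or period effect; two-sided 5% level; a juice effect t at the end of the juice period only.

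**Benchmark.** The paired end-of-period contrast has squared standard error 2(1−ρ)/N. Set t to give it 80% power; in large samples t = (1.96 + 0.84) × √(2(1−ρ)/N) = 2.80 × √(2(1−ρ)/N).

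**Group = genetic-information groups.** The group effect is not a beverage comparison, so no arithmetic applies.

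**Group = sequence.** Mean profiles over Weeks 1, 4, 7 and 10 are (0, t, 0, 0) for juice-first and (0, 0, 0, t) for placebo-first.
- Main effect: t/4 − t/4 = 0 for any t.
- Group-by-time: the difference profile is (0, t, 0, −t), one contrast inside a 3-df test. Omnibus power on F(3, 3(N−2)) at N = 18, 30, 42 is 0.625, 0.633, 0.637 if the 80% benchmark uses 3(N−2) error df, and 0.667, 0.657, 0.653 if it uses N−2.
- With *time* limited to Weeks 4 and 10, the interaction is the beverage contrast itself and nothing is lost.

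**Group = beverage, time = start and end of period, the two periods treated as different people.** The main effect averages start and end, so its size is t/2. Its true squared standard error is (1−ρ)/N, but the unpaired test uses (1+ρ)/N. The true standardised effect is 2.80/√2 = 1.98, and the effective critical value is 1.96 × √((1+ρ)/(1−ρ)).

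| ρ | Effective critical value | Large-sample power | Simulated power, N = 18, 30, 42 | Simulated type I error |
|---|---|---|---|---|
| 0.3 | 2.67 | P(Z > 0.69) = 25% | 0.276, 0.262, 0.254 | 0.8-1.0% |
| 0.5 | 3.39 | P(Z > 1.41) = 8% | 0.109, 0.097, 0.090 | 0.1-0.2% |
| 0.7 | 4.67 | P(Z > 2.69) = 0.4% | 0.014, 0.009, 0.007 | below 0.1% |

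Under this reading the group-by-time interaction compares within-period changes. Its squared standard error is 4(1−ρ)/N, so its standardised effect is again 1.98. Simulated type I error is 4.8-5.1% and power 52-54%.

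**Replacement contrast.** With period means π₁ and π₂ and juice effect τ, the expected Week 4 minus Week 10 difference is (π₁ − π₂) + τ for juice-first and (π₁ − π₂) − τ for placebo-first. Subtracting gives 2τ, so half the sequence coefficient estimates juice minus placebo and the period effect cancels.

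**Optional baseline covariate.** Under equal correlation, the covariance of (Week 1 − Week 7) with (Week 4 − Week 10) is ρ − ρ − ρ + ρ = 0. Simulated power with the covariate is then 0.769, 0.788, 0.785, a loss of about 1-3 points from 80%.

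**The case against.** The strongest reply is that group-by-time is an ordinary term of the stated model and that the sentence does not restrict testing to the group main effect. This stands. If *group* is sequence, the interaction is within-subject and contains the beverage contrast. A reader might infer that the plan's model cannot yield a valid test of juice against placebo; the documents do not support that. What they support is that the plan does not identify the definition of *group*, the levels of *time* or the term that would deliver the test.

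Three further points limit the concern.
- A reader might infer a raised false-positive risk from the unpaired reading. The opposite holds: type I error is 1% or less, so that test is conservative and the harm is lost power.
- The 1-28% figures belong to the main effect averaged over start and end of period, an unfavourable term. An unpaired test of end-of-period values alone does better. For an assumed 0.5 SD effect and correlations of 0.5-0.8, its power is 0.22-0.29 at N = 20 and 0.64-0.70 at N = 40, against 0.57-0.92 and 0.88-1.00 for the paired analysis. This is a different benchmark, so it is not comparable with the table.
- The visit table does list four visits for most outcomes, so *time* is partly answered. The analysis sentence does not refer to that table, and weight and blood pressure remain on another schedule.

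**Conclusion.** The concern holds as a contradiction within the text, not merely as missing detail. The randomisation rule refers to groups that the documents do not contain. The only stated comparison puts an undefined factor between subjects in a trial whose treatment factor is within subjects. Taken as the test of juice against placebo, the group effect is unrelated to beverage, zero by construction, or unpaired with heavy power loss. The interaction that could rescue the test is neither named nor tied to sequence.

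That conclusion rests on wording alone. The power figures depend on the assumed N, equal correlation and absence of carryover, and show scale only.

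Two other inferences go too far. The documents do not show that allocation was actually made on genotype: blocking on beverage order is the natural reading of the Protocol section, though it is unstated, and under 1:1 blocks order imbalance is not a material worry. Nor do they show where the genotype sentence came from. If the mismatch between the ANOVA and the crossover is also raised as a separate comment, its consequence should be counted once.

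**What to change.** 1. Delete the sentence on genotype and Groups 2 and 3. If genotyping does belong to this trial, define the groups and reconcile them with the crossover.
2. State that the PROC PLAN blocks allocate participants 1:1 to juice-then-placebo or placebo-then-juice.
3. Replace the ANOVA sentence with one named test: beverage is a single within-subject contrast on end-of-period values (Weeks 4 and 10), adjusted for period. Regress the Week 4 minus Week 10 difference on sequence; half the juice-first minus placebo-first coefficient estimates juice minus placebo. For complete pairs this equals a model with fixed participant effects and fixed period effects.
4. Optionally, prespecify the Week 1 minus Week 7 baseline difference as a covariate. It costs about 1-3 points of power if that difference is uncorrelated with the outcome difference, as equal correlation implies, and can gain power only under another correlation structure. It is not needed to repair the defect.

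The cost is rewording and a little analysis work. The allocation list needs regenerating only if it was built on a factor other than beverage order. No participants, visits or measurements are added.

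### The design is a two-period crossover, but the only planned test compares undefined groups between subjects, and no within-participant juice-minus-placebo contrast is named

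*Combined protocol and SAP*

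**What the plan says.** The Protocol section randomises participants to "either 100% watermelon juice or an isocaloric placebo for four weeks in a double-blind crossover design", with a two-week washout between periods. The visit table puts fasting blood, anthropometrics, FMD and PWV at four points: "Beginning of Week 1", the end of Week 4, "Beginning of Week 7" and the end of Week 10. A further line lists "Weekly: Weight, Blood Pressure, Adherence".

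The Statistical Analysis section has one sentence on inference: "Differences between groups will be evaluated by one-way ANOVA with repeated measures with group as the between-subjects factor", and time as the factor within subjects. It does not mention beverage, sequence or period, and it does not list the levels of time. The only groups it names appear in the randomisation text: "The randomization scheme will balance genotype in Groups 2 and 3", described there as people given genetic information at the start. The Protocol section contains no such groups.

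**The concern.** In a crossover each participant is their own control, so the juice effect is a within-participant quantity. A test of group differences with group between subjects does not target it. The sentence also allows several models: group could be sequence, beverage or genetic-information group, and time could have two levels or four. These models differ in degrees of freedom, error term and power, and some do not compare juice with placebo at all. With the choice left open, the test can be picked after the data are seen, or the literal group term can be reported as a null result for juice.

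**Working it through.** The plan states no sample size, power, alpha, SD or effect, so there is no figure of its own to reproduce. The check is algebra on the visit means, followed by an illustration on assumed inputs.

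**What each reading tests.** Let juice add t at the end of the juice period, with no carryover. Expected values at Weeks 1, 4, 7 and 10, apart from time effects common to both sequences, are:

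- juice first: (0, t, 0, 0)
- placebo first: (0, 0, 0, t)

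*Group = sequence.* Both rows average t/4, so the group main effect is t/4 − t/4 = 0 for any t. The row differences are (0, t, 0, −t), so juice appears only in group-by-time: 3 df with all four visits as levels, 1 df with Weeks 4 and 10 only.

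*Group = beverage.* The main effect averages start and end of period, which halves the effect to t/2, and it counts N people as 2N.

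*Group = genetic-information group.* The group term does not compare juice with placebo.

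**Assumed inputs.** N = 40, two-sided 5%, visits at days 0, 28, 42 and 70. The effect is set so that the unadjusted Week 4 minus Week 10 contrast has 80% power (noncentrality 8.27). Let r be the correlation between the Week 1 − Week 7 and Week 4 − Week 10 differences. Three types of covariance were used:

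- equal correlation 0.6: r = 0
- cross-period correlation 0.6 with within-period 0.64, 0.70 or 0.76: for example r = (2×0.64 − 2×0.6)/(2×0.4) = 0.10; the others give 0.25 and 0.40
- exponential decay with 14-day correlation 0.80, 0.90 or 0.95: r = 0.156, 0.239 or 0.285

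Rejection rates with the true effect present (40,000 simulated trials per setting):

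| Test | r=0 | 0.10 | 0.156 | 0.239 | 0.25 | 0.285 | 0.40 |
|---|---|---|---|---|---|---|---|
| Main effect, group = sequence | 0.049 | 0.050 | 0.049 | 0.052 | 0.050 | 0.049 | 0.052 |
| Main effect, group = beverage | 0.036 | 0.039 | 0.079 | 0.006 | 0.043 | 0.000 | 0.044 |
| Sequence-by-time, 3 df, Greenhouse-Geisser | 0.635 | 0.649 | 0.638 | 0.621 | 0.656 | 0.609 | 0.656 |
| Beverage-by-time, records as independent | 0.518 | 0.566 | 0.636 | 0.663 | 0.638 | 0.674 | 0.734 |
| Week 4 − Week 10, adjusted for Week 1 − Week 7 | 0.788 | 0.793 | 0.798 | 0.809 | 0.815 | 0.818 | 0.853 |

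The unadjusted end-value contrast gave 0.795–0.803, as set. At N = 24 the rows are about 5%, 0–9%, 60–65%, 53–68% and 78–81%.

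**Why the 3-df test loses power.** Under equal correlation ρ, with d the effect in SD units, the noncentrality is N·d²/(2(1−ρ)) for both the 3-df and the 1-df test. The same signal is spread over more degrees of freedom. To reach 80%, the 3-df test needs 32 participants where the 1-df contrast needs 24, or 56 where it needs 40.

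**Why the beverage main effect fails (ρ = 0.6).** d = √(8.27×2×0.4/40) = 0.407, so the tested difference is 0.407/2 = 0.203. The model's standard error is √(2×0.8/40) = 0.20, where 0.8 = (1+0.6)/2. The real one is √(0.4/40) = 0.10, because the two periods share a person. The ratio 0.203/0.20 is about 1, far short of significance.

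**False-positive rate.** Treating a person's two change scores as independent is harmless only if they are uncorrelated. Under the three decay settings they correlate at −0.14, −0.09 and −0.05, and null rejection was 0.066, 0.060 and 0.056. In the other four settings it was 0.049–0.051. The beverage main effect errs the other way, rejecting about 0–0.1% under the null. The 3-df test held 0.046–0.048 and the adjusted contrast 0.049–0.051.

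**The case against.** The plan never says that the group main effect is the test. A repeated-measures ANOVA with group and time reports group-by-time as a matter of course. If group is sequence, that interaction contains the juice effect and holds its error rate. Restricted to Weeks 4 and 10, it is exactly the right 1-df comparison. On this view the fault is under-specification, and the 5% and 0–8% figures describe the least favourable readings. This stands in part: the data can answer the question and one reading is sound. But the text does not select that reading, and what it does announce is a comparison of groups.

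The magnitudes rest wholly on assumed inputs, and 6.6% is the top of seven assumed settings. That is also right. The firm point is that the independence error moves the false-positive rate in either direction, depending on the test. Nor is any 1-df contrast automatically better: a within-participant comparison of change scores reached only 0.509–0.648 up to r = 0.285 (0.723 at r = 0.40).

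Finally, baseline adjustment is partly preference. It changes power by −1 to +2 points up to r = 0.29 and by about 5 at r = 0.40. The unadjusted end-value contrast would repair the main defect too, and a mixed model with treatment, period and sequence is a standard alternative that can keep incomplete participants.

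**Conclusion.** The concern holds, and the plan should be changed. The stated analysis does not fit the stated design: group is undefined, the only groups named do not belong to the crossover, and no within-participant juice-minus-placebo contrast is isolated. That the sequence main effect carries no juice effect is algebra and needs only the absence of carryover. The size is illustrative. With 40 participants and a contrast powered at 80%, the four-visit interaction drops to 61–66%, mostly through testing 3 df instead of 1. Beverage-by-time with records taken as independent has 52–67% (73% at r = 0.40). These figures depend on the assumed N, effect, alpha and correlations, none of which the documents give.

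**What to change.** Replace the ANOVA sentence with wording such as:

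> The comparison is juice versus placebo within participant. For each outcome measured at the four visits, the Week 4 minus Week 10 difference is regressed on sequence (juice first +1, placebo first −1) and on the Week 1 minus Week 7 difference. The sequence coefficient with its 95% CI is the juice-minus-placebo effect; the intercept takes up the period effect. For weekly weight and blood pressure, the readings at those same four time points are used.

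Remove the sentence on Groups 2 and 3 or reconcile it with the crossover, and state that the block randomisation allocates the order of beverages. The unadjusted Week 4 minus Week 10 contrast is an acceptable simpler choice, provided it is fixed in advance.

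This costs SAP wording only. The covariate uses one degree of freedom and brings little or no gain at low r. A participant missing any of the four visits drops out of the regression, and weekly readings between those points go unused. Carryover is not cured. If a fraction λ of the juice effect remains at Week 7 and a share s of that remains at Week 10, the relative bias is λ(r − s)/2, which can have either sign; for the unadjusted contrast it is −λs/2. The documents give no evidence on carryover.

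### Fitted classically over the four test visits, the repeated-measures ANOVA would exclude every incomplete participant, and the plan has no rule to prevent it; a mixed model with beverage and period would keep them

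*Combined protocol and SAP*

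**What the plan says.** The Protocol section describes a two-period crossover: participants receive "either 100% watermelon juice or an isocaloric placebo for four weeks in a double-blind crossover design". Its testing schedule has four visits for blood, anthropometrics, FMD and PWV, at the start and end of each regimen. The first regimen begins at "Beginning of Week 1" and the second at "Beginning of Week 7", after a two-week washout. Some measures are taken more often: "Weekly: Weight, Blood Pressure, Adherence".

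The Statistical Analysis section gives a single sentence on outcomes: "Differences between groups will be evaluated by one-way ANOVA with repeated measures with group as the between-subjects factor and time as the within-subjects factor". It does not name the fitting procedure, list the levels of time, or name beverage, period or sequence as a term. The sentence before it concerns genotype ("The randomization scheme will balance genotype in Groups 2 and 3"), so it is not certain what *group* refers to.

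No text defines an analysis set or deals with withdrawal, missed visits or imputation. The nearest is the adherence threshold, "Minimal adherence will be defined as 70% of recommended supplementation of two doses per day for four weeks", which carries no stated consequence for the analysis.

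**The concern.** Classical repeated-measures ANOVA works on complete profiles: a participant missing any level of the within-subjects factor is dropped. If the four test visits are the levels of time, someone who finishes the first regimen and then leaves contributes nothing. Someone who misses only the Week 7 visit is also lost, although both end-of-regimen values exist. For weight and blood pressure, measured weekly, a complete profile would need more than four values.

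Incomplete data are foreseeable. Participants are older adults who drink 24 ounces a day (two 12-ounce servings) in two separate four-week regimens, over about 12 weeks including run-in (2 + 10).

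Two things are at stake: first-period data that were randomised and already paid for, and the validity of a comparison restricted to people who completed both beverages.

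**Working it through.** The documents state no sample size, SD, dropout rate or within-person correlation, so there is no figure of the plan's own to reproduce. All rates below are assumptions.

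**1. Exclusion through sporadic missed visits.** Let p be the chance of missing any one visit, independent across visits. The share excluded is 1 − (1 − p)^4 if all four visits are required, and 1 − (1 − p)^2 if only the two end-of-regimen visits are.

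| p | all four required | two end-of-regimen visits required |
|---|---|---|
| 2% | 1 − 0.98^4 = 7.8% | 1 − 0.98^2 = 4.0% |
| 5% | 1 − 0.95^4 = 18.5% | 1 − 0.95^2 = 9.8% |
| 10% | 1 − 0.90^4 = 34.4% | 1 − 0.90^2 = 19.0% |

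**2. Data discarded through withdrawal after the first regimen.** If a fraction d leaves after two visits, the share of collected visits thrown away is 2d / [2d + 4(1 − d)]. For d = 10% this is 0.2/3.8 = 5.3%; for d = 20% it is 0.4/3.6 = 11.1%. Here the four-visit and two-visit rules exclude the same people, so the contrast between the columns in step 1 does not apply.

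**3. Bias when withdrawal is related to outcome.** Assume no true effect, values with SD 1 and within-person correlation ρ. The lowest 20% of period-1 values in the juice-first sequence leave, and nobody leaves the placebo-first sequence.
- The period-1 mean of the remaining juice-first participants rises by φ(z)/0.80 at the 20th percentile: 0.280/0.80 = 0.350 SD.
- Their period-2 mean rises by 0.350ρ, so their juice-minus-placebo difference is off by 0.350(1 − ρ).
- Averaging over the two sequences halves this, to 0.350(1 − ρ)/2.
- At ρ = 0.5: 0.350 × 0.5/2 = 0.0875, about 0.09 SD. At ρ = 0.7: 0.350 × 0.3/2 = 0.0525, about 0.05 SD.
- A likelihood fit that keeps the withdrawn participants' period-1 values restores the period-1 mean to 0 and estimates the period-2 mean as 0.350ρ − ρ(0.350 − 0) = 0. Its bias is about zero, because missingness here depends only on an observed value.

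A more severe scenario was simulated: true effect 1.00, between-subject and residual SDs both 1, the 30% of juice-first participants with the poorest change withdrawing, and 10% of placebo-first participants withdrawing at random. A mixed model on completers gave 1.17. The same model on all available visits gave 0.99 (SE 0.02).

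**4. Withdrawal that differs by beverage but is unrelated to outcome.** With 30% leaving at random after juice and 10% after placebo, the period-adjusted completer estimate was 1.00 against a true 1.00. With a period effect of 0.5 left unadjusted, completers are weighted 0.7/1.6 = 0.4375 juice-first and 0.9/1.6 = 0.5625 placebo-first. The bias is then 0.5 × (0.5625 − 0.4375) = 0.0625; simulation gave 1.07 with a uniform juice effect and 1.06 when it varied between people.

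**The case against.** A reader might infer that the plan requires all four visits. The documents do not establish that. If *group* means beverage and time means start and end of a regimen, the model needs two values per regimen. A participant who leaves after the first regimen would keep both, and a missed Week 7 visit would cost one regimen rather than the whole person. That would be a poor crossover analysis, since it places the same person in both levels of a between-subjects factor, but it is a possible reading. A likelihood-based repeated-measures fit would also keep partial data. This objection stands, and it makes the point conditional. It does not remove it: the plan permits deletion of incomplete participants and contains nothing to prevent it.

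A reader might also infer that any difference in withdrawal between beverages biases the result. It does not. Completers receive both beverages, so the period-adjusted within-person contrast stays unbiased when withdrawal is unrelated to outcome (step 4).

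The illustrations are also open to challenge. Selection on the lowest 20% in one sequence only is assumed. The trial is double-blind, and participants cannot readily perceive blood markers, FMD or PWV. The example is missing-at-random by construction, so the good performance of the likelihood estimate is built in. Participants with only one regimen also add limited information to a within-person contrast. All of this stands, and is why the figures show mechanism and order of size only.

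**Conclusion.** The point holds in conditional form. The plan's only outcome analysis has no beverage or period term and no handling of incomplete participants. Fitted classically over the four test visits, it excludes anyone with an incomplete profile. Data loss then follows directly. Bias needs a further condition: withdrawal related to outcome, or unequal losses between sequences combined with an unadjusted period effect. The second route is open here because the named model adjusts for neither period nor sequence in any stated way.

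Under the assumed rates, 8% to 34% of participants would be excluded, and the completer estimate would be off by about 0.05 to 0.09 SD in the moderate example. The documents neither support nor rule out those rates. Since a better-suited method costs almost nothing, the change should be made before analysis.

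**What to change.** Replace the ANOVA sentence with a linear mixed model for each outcome: participant as a random effect; beverage, period and sequence as fixed effects; fitted by likelihood to all available end-of-regimen values from all randomised participants. Use the regimen-start values already collected where they exist, without excluding anyone who lacks one. One way is to enter them as further responses with their own visit means, rather than as covariates. State what *group* means, and whether the genotype groups enter the model. Report withdrawals by beverage and period. Keep the analysis restricted to completers of both regimens as a sensitivity analysis.

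The cost is a few lines of analysis text and a different SAS procedure, with no extra visits, staff or participants. The small downside is that the estimate relies on a missing-at-random assumption, which should be stated; it is weaker than what the completer analysis needs.
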